### **3.2.5.1 Management of stomatitis/oral mucositis/mouth ulcers**

Stomatitis/oral mucositis/mouth ulcers due to Everolimus should be treated using local supportive care. Please note that investigators in earlier trials have described the oral toxicities associated with Everolimus as mouth ulcers, rather than mucositis or stomatitis. If your examination reveals mouth ulcers rather than a more general inflammation of the mouth, please classify the adverse event as such. Please follow the paradigm below for treatment of stomatitis/oral mucositis/mouth ulcers:

1. For mild toxicity (Grade 1), use conservative measures such as **non-alcoholic mouth wash or salt water (0.9%) mouth wash** several times a day until resolution.
2. For more severe toxicity (Grade 2 in which case patients have pain but are able to maintain adequate oral alimentation, or Grade 3 in which case patients cannot maintain

adequate oral alimentation), the suggested treatments are **topical analgesic mouth treatments (i.e., local anesthetics such as benzocaine, butyl aminobenzoate, tetracaine hydrochloride, menthol, or phenol) with or without topical corticosteroids**, such as triamcinolone oral paste 0.1% (Kenalog in Orabase®).

3. Agents containing hydrogen peroxide, iodine, and thyme derivatives (e.g. Thymol) may tend to worsen mouth ulcers. It is preferable to avoid these agents.
4. Antifungal agents must be avoided unless a fungal infection is diagnosed. In particular, systemic imidazole antifungal agents (ketoconazole, fluconazole, itraconazole, etc.) should be avoided in all patients due to their strong inhibition of Everolimus metabolism, thereby leading to higher Everolimus exposures. Therefore, topical antifungal agents are preferred if an infection is diagnosed. Similarly, antiviral agents such as acyclovir should be avoided unless a viral infection is diagnosed.

Note: Stomatitis/oral mucositis should be appropriately graded using the functional grading given on the NCI-CTC for adverse events, version 3.0.

### **3.2.5.2 Management of hyperlipidemia and hyperglycemia**

Treatment of hyperlipidemia should take into account the pre-treatment status and dietary habits. Blood tests to monitor hyperlipidemia must be taken in the fasting state. Treatment of hyperlipidemia should take into account the pre-treatment status and dietary habits. Blood tests to monitor hyperlipidemia must be taken in the fasting state.. Hyperlipidemia and hypertriglyceridemia should be treated according to local best clinical practice. Patients should be monitored clinically and through serum chemistry for the development of rhabdomyolysis and other adverse events as required in the product label/data sheets for HMG-CoA reductase inhibitors.

Hyperglycemia has been reported in clinical trials. Monitoring of fasting serum glucose is recommended prior to the start of everolimus therapy and periodically thereafter. Optimal glycemic control should be achieved before starting trial therapy.

### **3.2.5.3 Management of non-infectious pneumonitis**

Non-infectious pneumonitis is a class effect of rapamycin derivatives. Cases of non-infectious pneumonitis (including interstitial lung disease) have also been described in patients taking everolimus (see [Section 5](#) Adverse drug reactions). Some of these have been severe and on rare occasions, a fatal outcome was observed.

A diagnosis of non-infectious pneumonitis should be considered in patients presenting with non-specific respiratory signs and symptoms such as hypoxia, pleural effusion, cough or dyspnoea, and in whom infectious, neoplastic and other non-medicinal causes have been excluded by means of appropriate investigations. Patients should be advised to report promptly any new or worsening respiratory symptoms.

Patients who develop radiological changes suggestive of non-infectious pneumonitis and have few or no symptoms may continue everolimus therapy without dose alteration. If symptoms are moderate (Grade 2), consideration should be given to interruption of therapy until

symptoms improve. The use of corticosteroids may be indicated. Everolimus may be reintroduced at a reduced dose until recovery to Grade 1 or better.

For cases where symptoms of non-infectious pneumonitis are severe (Grade 3), everolimus therapy should be discontinued and the use of corticosteroids may be indicated until clinical symptoms resolve. Therapy with everolimus may be re-initiated at a reduced dose depending on the individual clinical circumstances.

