**Table 3.0 Everolimus dose level modification guidelines**

Dose level	Dose and schedule
0 (starting dose)	10 mg daily
-1	5 mg daily
-2	5 mg every other day

**Table 3-1 Criteria for dose-modification in case of suspected Everolimus  
Everolimus toxicity and re-initiation of Everolimus treatment**

Toxicity	Actions
Non-hematological toxicity	
Grade 2 (except pneumonitis – refer to Table 3-2)	If the toxicity is tolerable to the patient, maintain the same dose. If the toxicity is intolerable to patient, interrupt Everolimus until recovery to grade $\leq 1$ . Then reintroduce Everolimus at same dose. If event returns to grade 2, then interrupt Everolimus until recovery to grade $\leq 1$ . Then reintroduce Everolimus at the lower dose level.
Grade 3 (except hyperlipidemia*) (except pneumonitis – refer to Table 3-2)	Interrupt Everolimus until recovery to grade $\leq 1$ . Then reintroduce Everolimus at the lower dose level. For pneumonitis consider the use of a short course of corticosteroids.
Grade 4	Discontinue Everolimus.
Hematological toxicity	
Grade 2 Thrombocytopenia (platelets <math><75, \geq 50 \times 10^9/L</math>)	Interrupt Everolimus until recovery to grade $\leq 1$ ( $>75 \times 10^9/L$ ). Then reintroduce Everolimus at initial dose. If thrombocytopenia again returns to grade 2, interrupt Everolimus until recovery to grade $\leq 1$ . Then reintroduce Everolimus at the lower dose level.
Grade 3 Thrombocytopenia (platelets <math><50, \geq 25 \times 10^9/L</math>)	Interrupt Everolimus until recovery to grade $\leq 1$ (platelets $\geq 75 \times 10^9/L$ ). Then resume Everolimus at one dose level lower. If grade 3 thrombocytopenia recurs, discontinue Everolimus.
Grade 4 Thrombocytopenia (platelets <math><25 \times 10^9/L</math>)	Discontinue Everolimus.
Grade 3 Neutropenia (neutrophils <math><1, \geq 0.5 \times 10^9/L</math>)	Interrupt Everolimus until recovery to grade $\leq 1$ (neutrophils $\geq 1.5 \times 10^9/L$ ). Then resume Everolimus at the initial dose. If ANC again returns to Grade 3, hold Everolimus until the ANC $\geq 1.5 \times 10^9/L$ . Then resume Everolimus dosing at the lower dose level. Discontinue patient from study therapy for a third episode of grade 3 neutropenia.

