Grade 4 Neutropenia (neutrophils <math><0.5 \times 10^9/L</math>)	Interrupt Everolimus until recovery to grade $\leq 1$ (neutrophils $\geq 1.5 \times 10^9/L$ ). Then resume Everolimus at the lower dose level. If grade 3 or grade 4 neutropenia occurs despite this dose reduction, discontinue Everolimus.
Grade 3 febrile neutropenia (not life-threatening)	Interrupt Everolimus until resolution of fever and neutropenia to grade $\leq 1$ . Hold further Everolimus until the ANC $\geq 1,500/\text{mm}^3$ and fever has resolved. Then resume Everolimus at the lower dose level. If febrile neutropenia recurs, discontinue Everolimus.
Grade 4 febrile neutropenia (life-threatening)	Discontinue Everolimus.
Any hematological or non-hematological toxicity requiring interruption for $\geq 3$ weeks	Discontinue Everolimus.

\*Grade 3 hyperlipidemia (hypercholesterolemia and/or hypertriglyceridemia) should be managed using medical therapies (see Sec. 3.2.5.2).

Subjects who require anticoagulation after randomization should be treated according to their physician's discretion and can continue on study. Since everolimus can interact with warfarin, the use of low-molecular weight heparins or non-coumarin containing anticoagulants is encouraged. If warfain is administered, close monitoring of INR is warranted.

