**Table 3-5 Management of non-infectious pneumonitis**

Worst Grade Pneumonitis	Required Investigations	Management of Pneumonitis	Everolimus Dose Adjustment
Grade 1	CT scans with lung windows and pulmonary function testing including: spirometry, DLCO, and room air O2 saturation at rest. Repeat chest x-ray/CT scan every 2 Cycles until return to baseline.	No specific therapy is required	Administer 100% of Everolimus dose.
Grade 2	CT scan with lung windows and pulmonary function testing including: spirometry, DLCO, and room air O2 saturation at rest. Repeat each subsequent Cycle until return to baseline. Consider bronchoscopy *	Symptomatic only. Prescribe corticosteroids if cough is troublesome.	Reduce Everolimus dose until recovery to ≤ Grade 1. Everolimus may also be interrupted if symptoms are troublesome. Patients will be withdrawn from the study if they fail to recover to ≤ Grade 1 within 3 weeks.
Grade 3	CT scan with lung windows and pulmonary function testing including: spirometry, DLCO, and room air O2 saturation at rest; Repeat each subsequent Cycle until return to baseline. Bronchoscopy is recommended *	Prescribe corticosteroids if infective origin is ruled out. Taper as medically indicated.	Hold treatment until recovery to ≤ Grade 1. May restart protocol treatment within 3 weeks at a reduced dose (by one level) if evidence of clinical benefit. Patients will be withdrawn from the study if they fail to recover to ≤ Grade 1 within 3 weeks.
Grade 4	CT scan with lung windows and required pulmonary function testing includes: spirometry, DLCO, and room air O2 saturation at rest. Repeat each subsequent Cycle until return to baseline. Bronchoscopy is recommended *	Prescribe corticosteroids if infective origin is ruled out. Taper as medically indicated.	Discontinue treatment.

\*A bronchoscopy with biopsy and/or bronchoalveolar lavage is recommended.

All interruptions or changes to study drug administration must be recorded.

It will be documented whether or not each patient completed the clinical study. If for any patient either study treatment or observations were discontinued the reason will be recorded. Reasons that a patient may discontinue participation in a clinical study are considered to constitute one of the following:

1. adverse event(s)
2. abnormal laboratory value(s)

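### Section 3.2.5.3 and Table 3-5 give different dosing rules for Grade 2 and Grade 3 pneumonitis, nothing valid says which governs, and the table's retest interval is undefined

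*Combined protocol and SAP*

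**What the plan says.** Section 3.2.5.3 handles non-infectious pneumonitis twice, once in running text and once in Table 3-5.

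*Grade 2.* The text says: "If symptoms are moderate (Grade 2), consideration should be given to interruption of therapy until" symptoms improve. It then says: "Everolimus may be reintroduced at a reduced dose until recovery to Grade 1 or better". The table instead tells the site to reduce the dose until recovery to Grade 1 or better, and adds: "Everolimus may also be interrupted if symptoms are troublesome". It also sets a limit: "Patients will be withdrawn from the study if they fail to recover to" Grade 1 or better within 3 weeks.

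*Grade 3.* The text calls for discontinuation, with corticosteroids if indicated, and then says: "Therapy with everolimus may be re-initiated at a reduced dose depending on the individual clinical circumstances". The table says to hold drug until Grade 1 or better, and continues: "May restart protocol treatment within 3 weeks at a reduced dose (by one level) if evidence of clinical benefit". The same 3-week withdrawal limit applies.

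*Retesting.* Table 3-5 repeats imaging every two cycles at Grade 1, and imaging with lung function tests every cycle at Grades 2 to 4.

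*Related rules.* Section 3.2.3 bases dose changes for toxicity on Table 3-1. The Grade 2 and Grade 3 non-hematological rows of Table 3-1 exempt pneumonitis and refer to Table 3-2, as does section 1.1.3.3. Even so, the Grade 3 row ends: "Then reintroduce Everolimus at the lower dose level. For pneumonitis consider the use of a short course of corticosteroids". The last row of Table 3-1 reads "Any hematological or non-hematological toxicity requiring interruption for" three weeks or more, and the action is to discontinue everolimus. Section 3.2.4 takes a patient off study after a dose delay of more than 21 days. It also requires at least weekly follow-up when drug is interrupted or stopped for a suspected toxicity.

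**The concern.** The protocol describes pneumonitis as a class effect of rapamycin derivatives that has, rarely, been fatal. Its management should therefore be the same at every site, and two sites that each follow this section can act differently. One that works from the text may restart a Grade 3 patient without documented recovery to Grade 1, or leave a Grade 2 patient on full dose with no time limit. One that works from the table may do neither.

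The table also has two terms that this trial does not support. The cycle comes with no length. The clinical-benefit condition presumes a response that can be observed, and the trial treats patients who have no visible disease. What is at stake is patient safety and consistent conduct across sites.

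**Working it through.** No arithmetic is needed and the plan states no figure to reproduce. The check sets the rules side by side by grade, then looks for a statement of precedence, for other rules that close the gaps, and for a meaning of the two unclear terms.

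**1. Rules by grade**

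| Grade | Text of 3.2.5.3 | Table 3-5 | Same? |
|---|---|---|---|
| 1 | No dose change | Full dose | Yes |
| 2 | Consider interrupting; reduced dose only on reintroduction; no time limit | Reduce by default; interruption optional; withdraw if not at Grade 1 or better within 3 weeks | No |
| 3 | Discontinue; re-initiate at a reduced dose by individual circumstances; no recovery grade | Hold to Grade 1 or better; restart within 3 weeks, one level down, with a benefit condition; otherwise withdraw | No |
| 4 | Silent | Discontinue (as does Table 3-1) | No conflict |

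The conflict is confined to Grades 2 and 3.

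**2. Precedence.** No sentence ranks the text against the table. The pointer in Table 3-1 is the nearest thing to one, and it shows that a table was probably meant to govern. But no table in the document is numbered 3-2. Section 3.3.3 adds to the confusion by using the number 3-5 for a list of CYP3A4 drugs.

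**3. Do the general rules close the gaps?**

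- *Time limit, Grade 3.* Largely yes. A hold is an interruption, so the last row of Table 3-1 and section 3.2.4 cap it at about 3 weeks whichever rule a site follows.
- *Recovery grade, Grade 3.* No. Table 3-1 requires Grade 1 or better before restart after other Grade 3 non-hematological toxicity except hyperlipidemia, but exempts pneumonitis. Within the 3 weeks, the text alone sets no grade. On this one element it is weaker than the rule for an ordinary Grade 3 event.
- *Time limit, Grade 2 kept on drug.* No. Both general caps are triggered by interruption or delay. A patient never interrupted meets neither, so only Table 3-5 limits that patient.
- *Follow-up, Grade 2 kept on drug.* Only in part. Weekly follow-up under section 3.2.4 does not apply. Section 3.4.4.1 asks for assessment at each visit, or more often if needed.

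**4. Cycle.** As a time unit the word occurs only in Table 3-5. Section 3.3.1 prescribes continuous daily dosing. On-treatment visits are at weeks 4, 16, 32 and 52 (section 3.1), so the gaps are 4, 16 − 4 = 12, 32 − 16 = 16 and 52 − 32 = 20 weeks. They are unequal, and none can stand in for a cycle.

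**5. Clinical benefit.** Patients enter with no evidence of disease (section 3.2.2), treatment is double-blind (section 3.3.2), and drug stops at progression (section 3.3.1). A patient still on drug has no lesion to respond and no known assignment. One site could say the condition is never met, another that it is always met.

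**The case against.** The strongest reply is that governance is clear in substance. Section 3.2.3 leads to Table 3-1, Table 3-1 leads to a pneumonitis table, and only one exists, so the wrong number has one possible target. No pointer favours the text. This stands as evidence of intent. It does not settle the matter: the text remains in force beside the table, and section 3.2.5 itself describes Table 3-1 as general recommendations.

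A second reply is that the text is permissive and the table directive, so harm arises only if a site disregards the table. That is fair, and a site following the table would in practice satisfy the text. The reverse is not true, and the text contains nothing that sends its reader to the table.

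Several stronger readings are tempting, and the documents do not support them:

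- *That the text is looser throughout at Grade 3.* Its first action is to discontinue, which is firmer than a hold, and it links corticosteroids to resolution of symptoms. The gap is the missing recovery grade at restart.
- *That cases can be counted.* A reader might take the 2% listing in section 3.2.5 and compute 80 × 0.02 = 1.6 everolimus patients. But 2% is a reporting threshold for Grades 3 and 4 together, from a renal-cell trial with a median of 141 days on drug. No Grade 3 share or Grade 2 rate is given, and the result would count cases, not patients managed differently.
- *That most patients would miss the 3-week check.* With four visits, the 3 weeks before a visit cover 4 × 3 = 12 of 52 weeks (23%), which leaves 77% under uniform onset. But held and interrupted patients must already be followed weekly. The figure could concern only Grade 2 patients kept on drug, and section 3.4.4.1 allows extra assessments for them.
- *That the retest comes too late.* If a cycle were 4 weeks, the first retest would fall 4 − 3 = 1 week after the deadline. That length is assumed. The retest also runs until tests return to baseline, which is a different criterion from recovery to Grade 1, so a later retest does not prevent the 3-week rule from being applied.
- *That reduced dosing at Grade 2 before recovery is an error.* Both sources allow it.

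**Conclusion.** The concern holds in limited form. Text and table conflict at Grades 2 and 3, agree at Grade 1, and do not conflict at Grade 4. After allowing for the general rules, two gaps matter most: no recovery grade in the text before a Grade 3 restart, and no default reduction or time limit in the text for a Grade 2 patient kept on drug. The undefined cycle and the clinical-benefit condition mean that naming the table as governing is necessary but not sufficient.

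This rests on reading the text's Grade 2 interruption as optional, and the general 3-week caps as reaching interruptions and delays only. Both follow from the wording. A reader might infer an effect on the primary progression-free survival comparison. None is claimed, because the documents do not show how many patients would be managed differently. It is a patient-safety wording correction that should be made.

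**What to change.** In one protocol amendment:

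1. Change the Table 3-2 references in Table 3-1 and section 1.1.3.3 to Table 3-5, and state that Table 3-5 governs dosing for pneumonitis. Renumber the Table 3-5 reference in section 3.3.3 at the same time.
2. Align the section 3.2.5.3 text to the table. Grade 2: reduce by default, interruption optional, 3-week limit whether or not drug is interrupted. Grade 3: hold to Grade 1 or better, then restart within 3 weeks, one level down.
3. Replace the clinical-benefit condition with the investigator's judgement that restart is safe.
4. Replace the cycle with intervals in weeks, confirmed by clinicians, and require a recovery assessment for Grades 2 and 3 no later than week 3.

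Do not add a new rule on Grade 2 restart after interruption. Neither source contains one, and it would bar an interrupted patient from the reduced dose that an uninterrupted patient may take.

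The cost is protocol wording and its review. The sample size does not change. Fixed intervals may mean a few more imaging and lung function tests, only in patients with pneumonitis; the number cannot be stated because the present interval is undefined.

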**Table 3-5 Management of non-infectious pneumonitis**

Worst Grade Pneumonitis	Required Investigations	Management of Pneumonitis	Everolimus Dose Adjustment
Grade 1	CT scans with lung windows and pulmonary function testing including: spirometry, DLCO, and room air O2 saturation at rest. Repeat chest x-ray/CT scan every 2 Cycles until return to baseline.	No specific therapy is required	Administer 100% of Everolimus dose.
Grade 2	CT scan with lung windows and pulmonary function testing including: spirometry, DLCO, and room air O2 saturation at rest. Repeat each subsequent Cycle until return to baseline. Consider bronchoscopy *	Symptomatic only. Prescribe corticosteroids if cough is troublesome.	Reduce Everolimus dose until recovery to ≤ Grade 1. Everolimus may also be interrupted if symptoms are troublesome. Patients will be withdrawn from the study if they fail to recover to ≤ Grade 1 within 3 weeks.
Grade 3	CT scan with lung windows and pulmonary function testing including: spirometry, DLCO, and room air O2 saturation at rest; Repeat each subsequent Cycle until return to baseline. Bronchoscopy is recommended *	Prescribe corticosteroids if infective origin is ruled out. Taper as medically indicated.	Hold treatment until recovery to ≤ Grade 1. May restart protocol treatment within 3 weeks at a reduced dose (by one level) if evidence of clinical benefit. Patients will be withdrawn from the study if they fail to recover to ≤ Grade 1 within 3 weeks.
Grade 4	CT scan with lung windows and required pulmonary function testing includes: spirometry, DLCO, and room air O2 saturation at rest. Repeat each subsequent Cycle until return to baseline. Bronchoscopy is recommended *	Prescribe corticosteroids if infective origin is ruled out. Taper as medically indicated.	Discontinue treatment.

\*A bronchoscopy with biopsy and/or bronchoalveolar lavage is recommended.

All interruptions or changes to study drug administration must be recorded.

It will be documented whether or not each patient completed the clinical study. If for any patient either study treatment or observations were discontinued the reason will be recorded. Reasons that a patient may discontinue participation in a clinical study are considered to constitute one of the following:

1. adverse event(s)
2. abnormal laboratory value(s)
3. abnormal test procedure result(s)
4. disease progression
5. protocol violation
6. subject withdrew consent

7. lost to follow-up
8. administrative problems
9. death

### **3.3 Treatments**

#### **3.3.1 Everolimus Administration**

The study drug Everolimus or placebo will be self-administered (by the patients themselves). The investigator will instruct the patient to take the study drug exactly as specified in the protocol. Everolimus /placebo will be administered orally as once daily dose of 10 mg (two 5 mg tablets) continuously from study day 1 until progression of disease, unacceptable toxicity, or 1 year from start of therapy. Patients will be instructed to take Everolimus /placebo in the morning, at the same time each day. Everolimus /placebo can be taken with or without food (a low-fat meal is recommended). Dietary habits around the time of Everolimus /placebo intake should be as consistent as possible throughout the study. If vomiting occurs, no attempt should be made to replace the vomited dose. All dosages prescribed and dispensed to the patient and all dose changes during the study must be recorded.

Medication labels will comply with US legal requirements and be printed in English. They will supply no information about the patient. The storage conditions for study drug will be described on the medication label.

For this trial, Everolimus and placebo are supplied, by Novartis, 10 tablets per card. Tablets should be opened only at the time of administration as drug is both hygroscopic and light-sensitive. Drug request forms will be provided to use when ordering Everolimus and placebo. Everolimus will only be shipped once all required regulatory documents are received.

